## 6.2 Week 4 and week 8 visit

1. Participants will be asked to verbally confirm their willingness to continue in the study.
2. Any change in concurrent medications will be recorded.
3. Any adverse events occurring since the last clinic visit will be recorded.
4. A researcher will then examine the participant to ascertain the 28-joint tender and swollen counts, a patient visual analogue scale, and a physician visual analogue scale, required to assess disease activity using the DAS28-CRP score (Appendix A).
5. The participant will then complete a RADAI-5 questionnaire.
6. Remote self-entered RADAI-5 data will be reviewed on the ePROMs platform (see 6.4 below)
7. The pre-filled questionnaires provided to the participant at their last visit will be collected. If the participant has not had the opportunity to complete these or has not brought them to the appointment, then they will be asked to complete the questionnaires during the study visit:
  - a. Health Assessment Questionnaire Disability Index (HAQ-DI)
  - b. FACIT-F and MFS
  - c. PHQ-2
  - d. EQ-5D-5L
8. Participants will then be reminded on how to wear and activate the remote monitoring digital tracker devices, and how to access the ePROMs portal.
9. Participants will be provided with the following devices, to wear simultaneously for 7 days following the study visit:
  - a. Axivity AX6 monitor and adhesive dressing – for application to lower back
  - b. Axivity AX6 monitor and wrist strap – for application to wrist
  - c. VitalPatch self-adhesive monitor – for application to left upper chest wall
10. Blood tests will be taken as per below, thus avoiding additional hospital attendances for mandatory routine clinical blood monitoring during the study period. These results will be passed on to the local clinical DMARD monitoring service, and any necessary action taken by the local clinical team. In the event that a participant has blood monitoring more frequently than once every 4 weeks, then any blood tests required before the date of the next study visit will be performed by the clinical DMARD monitoring service as per usual routine practice.
  - a. Full Blood Count (FBC)
  - b. Erythrocyte sedimentation rate (ESR)
  - c. C reactive protein (CRP)
  - d. Urea and electrolytes (U&Es)

e. Liver function tests (LFTs)

11. Participants will be provided with the following documents at the end of the visit:
  - a. Blank paper questionnaires, for completion within the 48 hours prior to their next study visit
    - i. Health Assessment Questionnaire Disability Index (HAQ-DI)
    - ii. FACIT-F and MFS
    - iii. PHQ-2
    - iv. EQ-5D-5L
  - b. A pre-paid addressed envelope, to post back the reusable Axivity AX6 devices to the researcher team after 7 days

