### 4.2 Primary objectives

1. To assess the correlation and agreement between paired DAS28 and RADAI-5 measurements
2. To assess the longitudinal responsiveness and minimal detectable change in repeated RADAI-5 measurements
3. To assess the acceptability of remote PROM capture and activity/gait/heart rate monitoring, through the use of participant questionnaires and focus groups

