## **6. STUDY VISITS**

### 6.1 Initial study visit

Participants attending their initial appointment will undergo the following procedures.

1. All participants will have the opportunity to discuss the study further with a study investigator before signing the consent form.
2. Participant eligibility for study enrolment based on the inclusion and exclusion criteria will be confirmed.
3. Participants will be asked to provide baseline information including age, sex, address, telephone number, email address, past medical history, Clinical Frailty Score,[12] Charlson Comorbidity Index,[13] current medications, smoking status and alcohol intake.
4. The participant's height and weight will be recorded.
5. A researcher will then examine the participant to ascertain the 28-joint tender and swollen counts, a patient visual analogue scale, and a physician visual analogue scale, required to assess disease activity using the DAS28-CRP score (Appendix A).
6. The participant will then complete a RADAI-5 questionnaire (Appendix D).
7. The participant will then be asked to complete the following paper questionnaires:
  - a. Health Assessment Questionnaire Disability Index (HAQ-DI)
  - b. FACIT-F and MFS
  - c. PHQ-2
  - d. EQ-5D-5L
8. Participants will then be shown how to access the ePROMs portal. Written information will be provided to participants to explain this further.
9. Participants will then be instructed on how to wear and activate the remote monitoring digital tracker devices. Written information will be provided to explain this further. The following devices will be provided, and should be worn simultaneously for 7 days following the study visit:
  - a. Axivity AX6 monitor and adhesive dressing – for application to lower back
  - b. Axivity AX6 monitor and wrist strap – for application to wrist
  - c. VitalPatch self-adhesive monitor – for application to left upper chest wall
  - d. A study mobile phone and charger – for data linkage and downloading from the VitalPatch device

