## **8. DATA ANALYSIS**

### *8.1 Correlation between DAS28 and RADAI-5 measurements*

The correlation between paired DAS28 and RADAI-5 measurements taken at each study visit will be assessed by Pearson and Spearman correlation coefficients. DAS28 and RADAI-5 scores will also be dichotomised to binary disease activity values (e.g. high disease activity vs remission/low/moderate disease activity) based on published thresholds, and agreement between categorisation by DAS28 vs RADAI-5 scores assessed by Cohen's kappa statistic.

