#### APPENDIX D : RHEUMATOID ARTHRITIS DISEASE ACTIVITY INDEX 5 (RADAI-5)

The RADAI-5[1] is a self-completed questionnaire consisting of the following five questions, each scored on a 0-10 integer scale:

1. How active was your arthritis in the last six months? (anchors: 0 = completely inactive, 10 = extremely active)
2. How active is your arthritis today with respect to joint tenderness and swelling? (anchors: 0 = completely inactive, 10 = extremely active)
3. How severe is your arthritis pain today? (anchors: 0 = no pain, 10 = unbearable pain)
4. How would you describe your general health today? (anchors: 0 = excellent, 10 = extremely bad)
5. Did you experience joint (hand) stiffness on awaking yesterday morning? If yes, how long was this stiffness? (anchors: 0 = no stiffness, 10 = stiffness the whole day)

The mean value gives an overall “RADAI-5 score”, with validated disease activity thresholds[2]:

Disease activity	RADAI-5 thresholds
Remission	0.0-1.4
Mild	1.6 – 3.0
Moderate	3.2 – 5.4
High	5.6 – 10.0

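### RADAI-5 is completed straight after the 28-joint examination at every visit, so the reference assessment can influence the self-report it is paired with in the primary comparison

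*Protocol*

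**What the plan says.** The order is the same at every visit. In Protocol 6.1, item 5 begins "A researcher will then examine the participant to ascertain the 28-joint tender and swollen counts" and also collects the patient and physician VAS; item 6 follows with "The participant will then complete a RADAI-5 questionnaire (Appendix D". In 6.2 (weeks 4 and 8), item 4 is the examination and VAS step and item 5 is "The participant will then complete a RADAI-5 questionnaire". Section 6.3 (week 12) repeats items 4 and 5 in the same order.

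The first primary objective (4.2) is "To assess the correlation and agreement between paired DAS28 and RADAI-5 measurements". Section 8.1 says which pair is meant: "The correlation between paired DAS28 and RADAI-5 measurements taken at each study visit will be assessed by Pearson and Spearman correlation coefficients". The same scores are then dichotomised for Cohen's kappa.

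Appendix D makes RADAI-5 the mean of five 0-10 integer items. Item 2 asks "How active is your arthritis today with respect to joint tenderness and swelling", and item 3 asks about pain today. Appendix A builds DAS28-CRP from the tender and swollen counts, CRP and the patient VAS.

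Nothing in the protocol has the in-visit RADAI-5 completed before the examination or keeps one result from influencing the other. The other questionnaires (HAQ-DI, FACIT-F, MFS, PHQ-2, EQ-5D-5L) are meant to be filled in during the 48 hours before each follow-up visit.

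**The concern.** In a comparison of a self-report with a clinical reference, the self-report should not be open to influence from the reference. Here the participant has just had 28 joints examined for tenderness and swelling, and is next asked how tender, swollen and painful they are today. The examination may provoke tenderness and may draw attention to particular joints. Either would pass information from DAS28 to RADAI-5.

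This bears on the purpose of the pilot. The study summary describes the primary endpoint as remote methods against face-to-face DAS28-CRP, and the results are meant to support a later trial of remote monitoring. At home no examination precedes the questionnaire, so agreement measured just after one may not be the agreement seen in use. The order is fixed in the visit procedures, so no later analysis of the same pairs can remove its effect.

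**Working it through.** The protocol gives no figure that depends on this order, so there is none to reproduce. The sample of 20 is set by resources (5.4). The check has three parts.

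**1. Sensitivity of the scores (from Appendices A and D).** One point on one RADAI-5 item moves the score by 1/5 = 0.2. That is enough to go from 5.4 (top of moderate) to 5.6 (bottom of high), the split that 8.1 gives as its example. One point on each of items 2 and 3 moves the score by 2/5 = 0.4. A 10 mm change in patient VAS moves DAS28-CRP by 0.014 × 10 = 0.14.

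**2. Influence that follows the examination findings.** Work in SD units. Let ρ be the correlation without influence and c the carry-over, in SD of RADAI-5 per SD of DAS28. The observed score is R = R0 + c·D, so

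r = (ρ + c) / √(1 + c² + 2cρ).

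For a bivariate normal pair split at both medians, kappa = (2/π)·arcsin(r). Both ρ and c are assumptions.

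| c | r if ρ = 0.5 | r if ρ = 0.6 | r if ρ = 0.7 | kappa if ρ = 0.6 |
|---|---|---|---|---|
| 0 | 0.50 | 0.60 | 0.70 | 0.41 |
| 0.1 | 0.57 | 0.66 | 0.75 | 0.46 |
| 0.2 | 0.63 | 0.71 | 0.78 | 0.50 |
| 0.3 | 0.68 | 0.75 | 0.81 | 0.54 |

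For example, at ρ = 0.6 and c = 0.3: 0.9 / √(1 + 0.09 + 0.36) = 0.9 / 1.204 = 0.75.

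**3. A uniform shift, the same for everyone.** Adding a constant leaves Pearson and Spearman unchanged. Its effect on categories, for an assumed shift of 0.4 and RADAI-5 normal with assumed mean 4 to 5 and SD 1.8 to 2:

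- Moved into high: Φ((5.5 − m)/s) − Φ((5.1 − m)/s) runs from 0.065 (m = 4, s = 2) to 0.087 (m = 5, s = 1.8). With 20 × 4 = 80 pairs, all visits complete, that is about 5 to 7 pairs.
- Moved across any limit (1.5, 3.1 or 5.5): 14% to 17%.
- A shift of 0.2 moves 3% to 4% into high.

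Kappa at the high split moves in no fixed direction under this shift. At ρ = 0.7, m = 5, s = 2 and 20% high by DAS28, it falls from 0.38 to 0.33. At ρ = 0.7, m = 4, s = 1.8 and 50% high by DAS28, it rises from 0.32 to 0.39.

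Favourable bias in the correlation therefore needs the influence to track the findings (part 2). A uniform shift only relocates scores.

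**The case against.** The best defence has four parts.

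- **The mechanism is inferred.** The protocol does not say that findings are told to the participant. Item 2 is a single global rating with no joint list, given by people with established disease. Items 1, 4 and 5 (six months, general health, yesterday's stiffness) are less exposed. This stands: the influence is possible, not documented.
- **Reversal opens another path.** The patient VAS is a self-report inside DAS28-CRP, worth up to 0.014 × 100 = 1.4 points. If it followed RADAI-5, the participant could carry answers into the reference. This stands as a limit on the remedy but does not defeat it. The two self-reports are already adjacent under the current order; the place of the VAS should simply be fixed as well.
- **Unaffected data exist.** Section 6.4 collects RADAI-5 weekly on the portal, away from any study examination. This stands as mitigation, but 8.1 names the in-visit pair for the primary analysis.
- **It is an unpowered pilot.** At r = 0.6 with 20 independent pairs, the approximate 95% interval is tanh(atanh 0.6 ± 1.96/√17) = 0.21 to 0.82, wider than any shift shown above. This lowers the weight of the point. A bias still remains in the estimate passed to the next trial, whatever the sample size.

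A reader might infer more: that the two measures are known not to be independent, or that the number of pairs moved into the high category shows agreement to be inflated. The documents support neither. They contain no information on the size or form of any influence, and the category counts come from a uniform shift, which does not change the correlation.

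**Conclusion.** The point holds as a design weakness that should be corrected. It is neither a contradiction nor an error of calculation. The protocol fixes the examination before RADAI-5 at all four visits and makes that pair the data for the first primary objective, which exposes items 2 and 3 to influence in a way that remote use would not.

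The size is unknown. If the influence follows the findings, an assumed carry-over of 0.1 to 0.3 SD per SD of DAS28 turns a true correlation of 0.6 into 0.66 to 0.75, and a median-split kappa of 0.41 into 0.46 to 0.54. If it is the same for everyone, the correlation is unaffected and only category membership changes. Nothing in the protocol says which of these applies, or that either occurs.

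**What to change.** In 6.1 (after consent and eligibility), 6.2 and 6.3, place both self-reports, RADAI-5 and the patient VAS, before the joint examination. State their order and keep it the same at all visits. Add that the RADAI-5 form is set aside unseen by the joint assessor until the counts are recorded.

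As a check, add to 8.1 a comparison of DAS28-CRP with the nearest remote RADAI-5 entry before each follow-up visit. Section 6.4 already collects these entries. Portal access starts at the first visit, so at most 20 × 3 = 60 such pairs exist. A weekly entry may be several days old, so a lower correlation could reflect elapsed time as well as setting.

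The cost is a reordering of steps in three sections and one extra analysis on existing data, with no added procedure. The remaining limitation is that the patient VAS and RADAI-5 are still adjacent self-reports, as they are now.

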### 6.3 Week 12 visit

1. Participants will be asked to verbally confirm their willingness to continue in the study.
2. Any change in concurrent medications will be recorded.
3. Any adverse events occurring since the last clinic visit will be recorded.
4. A researcher will then examine the participant to ascertain the 28-joint tender and swollen counts, a patient visual analogue scale, and a physician visual analogue scale, required to assess disease activity using the DAS28-CRP score (Appendix A).
5. The participant will then complete a RADAI-5 questionnaire.
6. Remote self-entered RADAI-5 data will be reviewed on the ePROMs platform (see 6.4 below)
7. The pre-filled questionnaires provided to the participant at their last visit will be collected. If the participant has not had the opportunity to complete these or has not brought them to the appointment, then they will be asked to complete the questionnaires during the study visit:
  - a. Health Assessment Questionnaire Disability Index (HAQ-DI)
  - b. FACIT-F and MFS
  - c. PHQ-2
  - d. EQ-5D-5L
8. Participants will then be reminded on how to wear and activate the remote monitoring digital tracker devices, and how to access the ePROMs portal.
9. Participants will be provided with the following devices, to wear simultaneously for 7 days following the study visit:
  - a. Axivity AX6 monitor and adhesive dressing – for application to lower back
  - b. Axivity AX6 monitor and wrist strap – for application to wrist
10. Blood tests will be taken as per below, thus avoiding additional hospital attendances for mandatory routine clinical blood monitoring during the study period. These results will be passed on to the local clinical DMARD monitoring service, and any necessary action taken by the local clinical team. In the event that a participant has blood monitoring more frequently than once every 4 weeks, then any blood tests required before the date of the next study visit will be performed by the clinical DMARD monitoring service as per usual routine practice.
  - a. Full Blood Count (FBC)
  - b. Erythrocyte sedimentation rate (ESR)
  - c. C reactive protein (CRP)

- d. Urea and electrolytes (U&Es)
- e. Liver function tests (LFTs)

11. The study smartphone and charger will be collected from the participant.
12. Participants will be asked to complete a feedback questionnaire on acceptability of remote ePROMs and wearable digital monitoring devices. Participants will be asked whether they would be willing to take part in an optional focus group to discuss issues around acceptability of remote monitoring (see section 6.5 below).
13. Participants will be provided with the following documents at the end of the visit:
  - a. A pre-paid addressed envelope, to post back the reusable Axivity AX6 devices to the researcher team after 7 days

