### *5.5 Closure of study*

Recruitment to the study will close upon recruitment of the 20th participant or on 30/06/23, whichever is earlier. The study will close on 30/09/23.

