#### *6.5 Optional focus group*

Participants at their week 12 visit who express an interest in providing additional feedback on their experience of taking part in the study will be invited to take part in an optional focus group. Participants will join a meeting, either face-to-face or virtual, lasting for approximately 60 minutes. Individual (i.e. one-on-one) meetings may be arranged where participants would otherwise feel uncomfortable or inhibited in providing feedback in a group setting.

The session will be led by a study researcher, who will invite participants to reflect on their experience (positive and negative) of participating in the study, with a specific focus on:

1. Ease of use of ePROMs portal
2. Acceptability of frequency of ePROMs measurements
3. Ease of use and acceptability of Axivity AX6 and VitalPatch monitors

The meetings will not be recorded, but rather the researcher will take written notes during the meetings. Participant feedback may be transcribed verbatim, but participant feedback will be recorded in an anonymous fashion.

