#### *6.6 Participant autonomy*

Participants will have full autonomy throughout this study. The participant, informed of the full information as detailed in the participant information sheet, may withdraw their consent at any time. The wishes of the participant will be respected, and would result in them exiting the study at

that point. Any data collected up to that point would be retained and analysed by the study team in line with the terms of the original participant consent form.

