#### *6.8 End of study*

If the participant declines to take part in the optional focus group (section 6.5), then the week 12 visit will be their final study visit. The participant will exit the study 7 days after this visit (i.e. at the end of their final remote monitoring device measurement period).

If the participant agrees to take part in the optional focus group (section 6.5), then a further optional focus group visit will occur no later than 180 days from the date of their week 12 visit. No additional study visits are permitted between the week 12 and optional focus group visits. No blood monitoring or disease activity measurements (remote or otherwise) will be performed as part of the research study beyond 7 days after the week 12 visit. The participant will exit the study at the end of the optional focus group visit.

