#### *8.4 Participant acceptability*

Quantitative feedback from participant acceptability questionnaire Likert scales will be summarised (median/mode and range). Anonymised free text responses will be reproduced verbatim, analysed for common themes and presented in tabular form. Anonymised field notes from the optional focus group meeting will be explored for common themes, and summarised in a tabular form with verbatim quotes as necessary. The focus of these analyses is to gather information around participant acceptability for the purposes of improving the design of our future research studies, rather than to generate generalizable data and results suitable for a qualitative research publication.

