## 15. SCHEDULE OF EVENTS

Activity	Visit 1: day 0	Visit 2: Day 28 (+/- 7 days)	Visit 3: Day 56 (+/- 7 days)	Visit 4: Day 84 (+/- 7 days)	Optional Focus Group (<180 days)
Informed consent	X				
Study eligibility assessment	X				
Medical history	X				
Clinical frailty score	X				
Charlson Comorbidity Index	X				
Height and weight	X				
Concomitant medications	X	X	X	X	
Adverse event recording and reporting		X	X	X	
Joint counts / VAS scores	X	X	X	X	
RADAI-5	X	X	X	X	
HAQ-DI	X	X	X	X	
FACIT-F	X	X	X	X	
MFS	X	X	X	X	
PHQ-2	X	X	X	X	
EQ-5D-5L	X	X	X	X	
Register on ePROMs portal	X				
Instruction on use of remote monitoring devices	X				
Provision of study smartphone and charger	X				
Review of ePROMs record		X	X	X	
Provision of monitoring devices and pre-paid envelope	X	X	X	X	
Collection of study smartphone and charger					X
Bloods (CRP, ESR, FBC, U&Es, LFTs)	X	X	X	X	
Provision of paper questionnaires for next visit	X	X	X		
Experience feedback questionnaire				X	
Optional focus group					X

CRP: C-reactive protein, ESR: erythrocyte sedimentation rate, EQ-5D-5L: EuroQol 5D-5L, FACIT-F: Functional Assessment of Chronic Illness Therapy – Fatigue, FBC: full blood count, HAQ-DI: Health Assessment Questionnaire Disability Index, LFTs: liver function tests, MFS: Mental Fatigue Scale, PHQ-2: Patient Health Questionnaire 2, RADAI-5: Rheumatoid Arthritis Disease Activity Index 5, U&Es: urea and electrolytes.

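### Acceptability (primary objective 3) is measured only in participants who attend week 12; the plan asks early leavers for no rating and no reasons

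*Protocol*

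**What the plan says.** Section 4.2 of the Protocol lists as its third primary objective: "To assess the acceptability of remote PROM capture and activity/gait/heart rate monitoring, through the use of participant questionnaires and focus groups". It names two instruments, and both are tied to the week 12 visit.

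- **Questionnaire.** Section 6.3, item 12: "Participants will be asked to complete a feedback questionnaire on acceptability of remote ePROMs and wearable digital monitoring devices". Sections 6.1 and 6.2 (initial, week 4 and week 8 visits) contain no such item. In the schedule of events (section 15) the row "Experience feedback questionnaire" has one mark, under Visit 4, day 84 ± 7 days.
- **Focus group.** Section 6.5 limits the invitation to interested week 12 attenders; its sentence begins: "Participants at their week 12 visit who express an interest in providing additional feedback on their experience of taking part in the study will be".

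On withdrawal, section 6.6 says "The wishes of the participant will be respected, and would result in them exiting the study at" that point. Data already collected are kept and analysed. No exit questionnaire or interview is described.

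On analysis, section 8.4 says "Quantitative feedback from participant acceptability questionnaire Likert scales will be summarised" by median or mode and range. It does not mention people who were never given the form.

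On dates, section 5.5 ends recruitment at the 20th participant or on 30/06/23, whichever comes first, and adds: "The study will close on 30/09/23". Section 6.8 says that if a participant agrees to the focus group, "then a further optional focus group visit will occur no later than 180 days from the date of their week 12 visit", and that the participant exits at the end of that meeting.

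**The concern.** People who find the portal or the devices burdensome are the ones with most to say about acceptability, and they may also be the ones most likely to stop. A questionnaire given only to those still attending at week 12 leaves them out by design. Entry is already restricted to people willing to commit to the monitoring (section 5.1, criterion 4), so measuring acceptability only in completers adds a second selection in the same direction.

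The gap lies in data collection. A statistical analysis plan can define denominators, but it cannot recover ratings or reasons that nobody asked for, so the timing has to be settled in the Protocol. What is at stake is the acceptability evidence meant to help shape the future trial.

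A second, unrelated matter is that the fixed closing date does not fit the focus group limit or the upper end of the week 12 visit window for late recruits.

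**Working it through.** **1. Who can contribute acceptability data**

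| Participant | Questionnaire (6.3, item 12) | Focus group invitation (6.5) | Other information in the plan |
|---|---|---|---|
| Attends week 12 | Yes | Yes, if interested | Full data |
| Leaves before week 12 | No | No | Data up to exit (6.6); discussion of missing portal entries at any monthly visit attended (6.4, item 3) |
| Never enrols | No | No | Screening log of technological barriers (section 9) |

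The middle row is the gap. Data retained from early leavers hold no acceptability rating, because none is taken before week 12. The monthly discussion covers access to and use of the portal, not the wearables.

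**2. Possible size (illustration only)**

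The Protocol gives no dropout rate and no expected rating, so there is no stated figure to reproduce. Let N = 20 (section 5.4), m = number leaving early, p = proportion favourable among completers, q = proportion of leavers who would have been favourable. Then

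completer result − all-enrolled result = p − [p(N − m) + qm]/N = (p − q) × m/N.

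Assume p = 0.80 to 0.90 and, as the unfavourable extreme, q = 0:

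- m = 0: 0 points
- m = 1: 0.80 × 1/20 to 0.90 × 1/20 = 4 to 4.5 points
- m = 2: 0.80 × 2/20 to 0.90 × 2/20 = 8 to 9 points
- m = 4: 0.80 × 4/20 to 0.90 × 4/20 = 16 to 18 points

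In whole participants with m = 4: 14/16 = 87.5% among completers against 14/20 = 70% of all enrolled, a gap of 17.5 points. If leavers would have rated as completers do (q = p), the gap is zero whatever m is.

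Section 8.4 plans a median or mode and a range, not a proportion favourable. With 14 of 20 favourable, the median still falls in the favourable part of the scale. The lower end of the range is more exposed, since it is set by the least satisfied respondent.

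**3. Dates**

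Inputs: last enrolment 30/06/23 and closure 30/09/23 (5.5); visit 4 on day 84 ± 7 (section 15); 7 days of device wear after it (6.3); focus group within 180 days of it (6.8). For enrolment on 30/06/23:

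| Visit 4 on day | Date | Device week ends | Days from visit to closure | 180-day limit |
|---|---|---|---|---|
| 77 | 15/09/23 | 22/09/23 | 15 | 13/03/24 |
| 84 | 22/09/23 | 29/09/23 | 8 | 20/03/24 |
| 91 | 29/09/23 | 06/10/23 | 1 | 27/03/24 |

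- Last enrolment for which the full 180 days fit after a day-84 visit: 30/09/23 − (84 + 180) days = 09/01/23 (02/01/23 to 16/01/23 for visits on day 91 to day 77).
- Last enrolment for which a day-91 visit and its device week fit: 30/09/23 − (91 + 7) days = 24/06/23.

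Visit 4 itself always falls before closure, so the closing date does not affect the questionnaire.

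**The case against.** A reader might infer that early leavers are never counted. The Protocol does not support that. Their data up to exit are kept (6.6), missing portal entries are discussed at each monthly visit to find difficulties (6.4), willingness to continue is asked at weeks 4 and 8 (6.2), and withdrawals can be counted against the number enrolled. What is missing is narrower: their rating of acceptability and their reasons for stopping.

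A reader might also infer that feasibility is overstated. That is not shown. The direction depends on dropout occurring and on its being related to burden, and the Protocol gives neither a dropout rate nor a feasibility threshold. Section 8.4 also limits these analyses to improving future study design and disclaims generalisable results. That lowers the consequence. It does not remove it, because reasons for stopping are directly useful for that purpose and acceptability is still listed as a primary objective.

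Completion counts over all enrolled, with confidence intervals, may well stand in an analysis plan that is not at hand. Their absence is no finding.

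On the dates, it is tempting to say that closure removes the focus group for late recruits. It does not. The 180 days are a maximum, the meeting takes about 60 minutes and may be virtual or one-to-one (6.5), and 1 to 15 days remain even for the last possible recruit. The problem shrinks or disappears if the 20th participant enrols early. Nor do the dates add to the selection described above: late recruits are not early leavers. The device-week overrun needs both enrolment after 24/06/23 and a late visit 4.

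**Conclusion.** The point holds in a limited form. Both instruments named for primary objective 3 reach only participants who attend week 12, and nothing is offered at withdrawal. Followed exactly, the plan yields acceptability data from completers only. The summary is likely to be biased upward if dropout is related to burden.

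The size cannot be derived from the Protocol. The illustrative 8–9 points with 2 leavers and 16–18 with 4 rest on assumed completer ratings of 80–90% favourable and on counting every leaver as unfavourable. The gap is zero if nobody leaves or if leavers would have rated like completers. The conclusion concerns the acceptability summary, not every feasibility measure.

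The date conflict is separate and minor. Sections 5.5, 6.8 and 15 cannot all be used to their stated limits: the 180-day allowance is unavailable in full to anyone enrolled after about 09/01/23 (day-84 visit), and the final device week can run to 06/10/23, after closure.

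**What to change.** 1. **Collect the missing responses.** In sections 6.3 and 6.6, and in the schedule of events, add that the same feedback questionnaire is offered, on a voluntary basis, when a participant withdraws or misses the week 12 visit, with space for reasons for stopping. Section 6.6 should make clear that declining it has no effect on the right to leave at once.
2. **Show the denominator.** In section 8.4, state that the number responding will be given out of all enrolled, and that early leavers' responses will be shown separately from those of week 12 attenders.
3. **Reconcile the dates.** Bring sections 5.5, 6.8 and 15 into line: either adjust the closing date, or shorten the focus group window and state the last enrolment date that fits closure on 30/09/23.

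The cost is one more use of an existing form, one sentence of reporting and a date amendment. Some people who leave will not answer, so the gap will be reduced and not closed. Reporting how many were asked and how many replied makes what remains visible.
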